3.7.1.4 Biomarker analyses

Total IgE in serum and fungal-specific IgE in serum will be summarized in the safety population. Baseline values will be the last value collected prior to the first IMP. Descriptive statistics (including number, mean, SD, median, Q1, Q3, min, max) of biomarkers at baseline and each post-baseline visit will be summarized.

Summary plots (mean +/- standard error of the mean) on values at each visit, changes from baseline and percent changes from baseline will be provided for the total IgE in serum and fungal-specific IgE in serum by intervention group and visit.

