[REDACTED] Reduction in serum IgE level may be a biomarker for the control of type 2 inflammation. Based on previous research, increase in total serum IgE level of 10% or more in patients with AFRS after surgery might be helpful to detect recurrence of sinus disease and predict the need for recurrent sinus surgery (34). Therefore, change in total IgE and fungal-specific IgE will be measured as secondary endpoints.

The proposed study design and endpoints will answer important clinical questions regarding the ability of dupilumab to reduce the need of SCS rescue therapy and surgery, objective signs of the disease, and symptoms reported by patients, which are the most relevant clinical practice assessments and reflect current standard of care. Forced expiratory volume (FEV1) and asthma control questionnaire 6-item version (ACQ-6) questionnaire will be used in AFRS patients with asthma for lung function and symptom improvement.

Other efficacy assessments based in Patient-Reported Outcomes (PRO) including health-related quality of life (HRQoL) using the specific HRQoL 22-item sino-nasal outcome test (SNOT-22) instrument will also be measured to evaluate the potential real life benefit.

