The change from baseline to Week 24 and Week 52 in the continuous secondary endpoints will be analyzed using the same analysis approach as for the primary endpoint of change from baseline in LMK score at Week 52.

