
• To evaluate the efficacy of dupilumab in improving sense of smell in participants with AFRS• To explore the effect of dupilumab as assessed by three-Dimensional CT volumetric measurement of the paranasal sinuses• To evaluate the safety and tolerability of dupilumab when administered to participants with AFRS• To evaluate the PK of dupilumab in participants with AFRS• To characterize the effect of dupilumab on total IgE and fungal-specific IgE• To assess immunogenicity to dupilumab in participants with AFRS	
• Change from baseline in monthly average total symptom score (TSS) derived from the Nasal Symptom Diary at Week 24 and Week 52• Change from baseline in visual analog scale (VAS) rhinosinusitis at Week 24 and Week 52• Change from baseline in University of Pennsylvania smell identification test (UPSIT) at Week 24 and Week 52• Change from baseline in the score of decreased/loss of smell using the Nasal Symptom Diary at Week 24 and Week 52• Change from baseline to Week 52 in three-Dimensional CT volumetric measurement of the paranasal sinuses• Incidence of treatment-emergent adverse events (TEAEs) or serious adverse events (SAEs) through Week 52• Dupilumab concentration in serum over time• Percent change from baseline in total IgE in serum compared with placebo over the 52-week treatment period• Percent change from baseline in fungal-specific IgE in serum compared with placebo over the 52-week treatment period• Assessment of incidence of treatment-emergent anti-drug antibodies (ADA) to dupilumab over time

Objectives	Endpoints

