3.3 SECONDARY ENDPOINT(S) ANALYSIS

The secondary endpoints detailed in this section are secondary efficacy endpoints and selected secondary biomarker endpoint. Other secondary endpoints analyses are defined in [Section 3.6.2](#) (AE, SAE), [Section 3.7.1.1](#) (PK), [Section 3.7.1.2](#) (immunogenicity) and [Section 3.7.1.4](#) (biomarker).

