3.3.1.2 Main analytical approach

Continuous secondary efficacy endpoints

Continuous secondary efficacy endpoints will be analyzed similarly as primary estimand of primary endpoint.

[figure not shown]
Percent change from baseline in total IgE in serum at Week 52

[figure not shown]
This secondary endpoint will be analyzed similarly as primary estimand of primary endpoint, and will be performed on safety population.

[figure not shown]
Proportion of participants who receive SCS and/or undergo/plan to undergo surgery for AFRS during the planned study treatment period

[figure not shown]
This secondary endpoint will be analyzed with the primary estimand defined according to the following attributes:

[figure not shown]
- Endpoint: Proportion of participants who receive SCS and/or undergo/plan to undergo surgery for AFRS during the planned study treatment period
- Treatment condition: dupilumab will be compared to placebo
- Analysis population: ITT population
- Intercurrent events (IE):
 - The following IEs will be handled with a treatment policy strategy:
 - Discontinuation of study intervention
 - Taking antifungals or other prohibited/rescue medications
- Population-level summary
 - After the implementation of IE handling strategy,
 - Missing data handling: Participant who discontinue the study prior to Week 52 without an event will be considered as no event.
 - Risk difference between interventions as well as the corresponding 95% confidence interval (CI) will be estimated using Mantel-Haenszel estimate and confidence limits, with Mantel-Haenszel stratum weights for time from last surgery (≤ 2 years, > 2 years) and region (Americas, Asia) and the Sato variance estimator. The P-value associated with Mantel-Haenszel method will be provided.
 - Descriptive statistics including number and proportion of participants with events will be provided for each intervention group.

[figure not shown]

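### Fungal-specific IgE is a secondary endpoint defined against placebo, but the SAP plans no between-arm estimate or confidence interval for it

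*SAP*

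**What the plan says.** The objective in SAP Table 1 is "To characterize the effect of dupilumab on total IgE and fungal-specific IgE". It carries two IgE endpoints, each a percent change set against placebo. The second is "Percent change from baseline in fungal-specific IgE in serum compared with placebo over the 52-week treatment period", and Protocol Table 1 has the same wording. Protocol 3.1 confirms their standing: "change in total IgE and fungal-specific IgE will be measured as secondary endpoints".

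SAP 3.3 sets the scope of the model-based analyses: "The secondary endpoints detailed in this section are secondary efficacy endpoints and selected secondary biomarker endpoint". Other biomarker endpoints are referred to section 3.7.1.4. The one selected biomarker endpoint is "Percent change from baseline in total IgE in serum at Week 52", which SAP 3.3.1.2 analyses in the same way as the primary endpoint, on the safety population.

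For fungal-specific IgE, section 3.7.1.4 offers "Descriptive statistics (including number, mean, SD, median, Q1, Q3, min, max) of biomarkers at baseline and each post-baseline visit will be summarized". It adds plots of mean plus or minus standard error, by arm and visit, for values, changes and percent changes.

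**The concern.** An endpoint whose definition contains a comparison with placebo needs an analysis that delivers one. Followed as written, the SAP would report by-arm summaries and curves for fungal-specific IgE, but no statement of how far the arms differ or how precisely that is known. Fungal-specific IgE reflects sensitisation to the organism that drives this disease, so readers will want that number.

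There is a particular reason to want the contrast. The Schedule of Activities says that only allergen-specific IgE results positive at screening are retested. Values selected for being positive may fall somewhat on repeat measurement in both arms. Randomisation allows that shared change to be subtracted, but the SAP does not specify the subtraction.

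**Working it through.** No arithmetic applies: the documents state no effect size, standard deviation or power for this endpoint. The check is to follow the two IgE endpoints through the plan side by side.

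| Place | Total IgE | Fungal-specific IgE |
|---|---|---|
| Protocol Table 1, SAP Table 1 | Secondary, defined against placebo | Secondary, defined against placebo |
| SAP Table 2, objectives listed | Named | Named |
| SAP Table 2, estimand rows | Own row: safety population, ANCOVA, WOCF, multiple imputation | No row |
| SAP 3.3.1, list of endpoints | Listed, Week 52 | Not listed |
| SAP 3.3.1.2, method | As for the primary endpoint | Not mentioned |
| SAP 3.5, hierarchy | Last of 14 | Absent |
| SAP 3.7.1.4 | Descriptive statistics, by-arm plots | Descriptive statistics, by-arm plots |

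Three further checks:

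1. *Does a general row reach it?* SAP Table 2 has a row for continuous secondary efficacy endpoints. SAP 3.3.1 enumerates those endpoints and fungal-specific IgE is not among them, so the row does not apply.
2. *Is the endpoint itself tabulated?* The descriptive sentence in 3.7.1.4 refers to the biomarkers at baseline and each later visit. Percent change, which is the endpoint, is named only for the plots.
3. *Could the analysis be in text that is not public?* Section 3.7.1.3 is not shown, but SAP 3.3 sends biomarker endpoints to 3.7.1.4, which is. Redaction is an unlikely explanation.

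Result: of two IgE endpoints defined against placebo, one has a specified between-arm estimate and the other has none.

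The number who would contribute cannot be derived. About 62 are to be randomised. Protocol 5.1 (I 02) accepts a positive skin test in place of positive serum fungal-specific IgE, and only serum-positive allergens are retested, so some participants may have no follow-up value.

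**The case against.** The strongest reply is that this was a choice. SAP 3.3 speaks of a selected biomarker endpoint, total IgE was the one selected, and other secondary endpoints (PK, immunogenicity, adverse events) are also handled descriptively. Secondary status does not by itself require inference, and the hierarchy covers only selected endpoints. All of that stands: absence from the hierarchy is not an error. It does not explain why the definition still sets this endpoint against placebo, or why Table 2 still lists its objective without a matching row.

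A reader might infer that no randomised comparison will be visible at all. The documents do not support that. SAP 3.1 makes output by intervention group the default, and the 3.7.1.4 plots show the concurrent placebo arm, so a fall common to both arms would be seen. A reader could even approximate an unadjusted difference, with standard error equal to the square root of the sum of the two squared standard errors. That is a makeshift: 3.7.1.4 states no covariate adjustment, intercurrent-event rule or missing-data rule.

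A reader might also infer that the SAP silently dropped an analysis the protocol required. Protocol 9.4.3 does say "The change from baseline to Week 24 and Week 52 in the continuous secondary endpoints will be analyzed using the same analysis approach", meaning the ANCOVA of the LMK score, and none of the three changes in the SAP's version history concerns IgE. But 9.4.3 opens by limiting itself to efficacy endpoints, and 9.4.6 leaves exploratory biomarker analyses to the SAP. Against that, this endpoint is labelled secondary, not exploratory. Both readings are tenable, so an unrecorded departure is not established.

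**Conclusion.** The point holds in limited form. A stated secondary endpoint, comparative by definition, has no planned effect estimate, confidence interval or model, while its companion endpoint has all of these. What is lost is the size of the treatment effect on fungal-specific IgE and its uncertainty. The display of the placebo arm is not lost.

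The conclusion rests on the text of the two documents and on no numerical assumption. It would be tempting to add that the trial has ample power for this comparison. The documents do not support such a claim: any figure would need an assumed standard deviation and an assumed number of participants with a screening-positive serum result, and taking the full 31 per arm could overstate that number.

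The consequence is modest. The primary analysis, the hierarchy and trial conduct are unaffected. It is worth correcting because the correction is cheap.

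**What to change.** In SAP Table 2 and 3.3.1.2, add percent change from baseline in fungal-specific IgE at Week 52 to the between-arm analysis planned for total IgE:

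- safety population, same ANCOVA covariates, same WOCF and multiple-imputation rules;
- dupilumab-minus-placebo difference with 95% CI and a nominal p-value, stated to be outside the hierarchy;
- one value per participant, combining that participant's screening-positive fungal allergens by a rule fixed in advance (for example, the mean of the allergen-level percent changes), so that several allergens from one person are not counted as independent;
- analysis restricted to participants with at least one screening-positive fungal allergen, with that number reported by arm.

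A log-scale geometric mean ratio may be added as a sensitivity analysis. The descriptive tables and plots stay.

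The cost is SAP wording, one model and one table, using samples already scheduled at screening and Weeks 12, 24 and 52. The small downside is one more non-confirmatory comparison. If the sponsor intends description only, the consistent alternative is to remove the reference to placebo from the endpoint, label it descriptive and record that in the table of modifications. That would leave the treatment effect unquantified.

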3.7.2 Subgroup analyses

Subgroup analyses of the primary efficacy endpoint will be performed to assess the homogeneity of the treatment effect across the following subgroups (categories with fewer than 5 participants may be combined with other categories):

- Age group (<40, \geq 40 years)
- Gender (Male, Female)
- Region (Americas: Argentina, USA, Canada; Asia: China, Japan, India, Turkey, Saudi Arabia)
- Race (White, Asian and Other)
- Ethnicity (Hispanic or Latino or unknown, Not Hispanic or Latino)
- Baseline weight (<70, \geq 70- <90, \geq 90 kg)

- Baseline BMI (<27 , ≥ 27 kg/m 2)
- Time from last surgery (≤ 2 years [including surgery naive participants], >2 years)
- Asthma comorbidity (Yes, No), identified as investigator reported in the eCRF.

The subgroup analyses will be performed based on imputed datasets from the primary analysis. Treatment-by-subgroup interaction term and the subgroup factor term will be added in the primary model. In the case that the subgroup factor is identical or similar to a randomization strata factor adjusted in the main model already, the strata factor will not be kept in the model. Statistical inference obtained from all imputed data will be combined using Rubin's rule.

In each subgroup, the treatment effects (dupilumab versus placebo) for the primary endpoint will be provided, as well as the corresponding 95% CI, using the same method as applied to the primary analysis. Forest plots will be provided.

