10.1.4 Data protection

All personal data collected related to participants, Investigators, or any person involved in the study, which may be included in the Sponsor's databases, shall be treated in compliance with all applicable laws and regulations including the GDPR. The study Sponsor, Sanofi is responsible for ensuring compliance with this matter, when processing data from any individual who may be included in the Sanofi databases, including Investigators, nurses, experts, service providers, Ethics Committee members, etc.

When archiving or processing personal data pertaining to the Investigator and/or to the participants, the Sponsor takes all appropriate measures to safeguard and prevent access to this data by any unauthorized third party.

Protection of participant data

Data collected must be adequate, relevant and not excessive, in relation to the purposes for which they are collected. Each category of data must be properly justified and in line with the study objective.

Participant race and ethnicity will be collected in this study because these data are required by regulatory agencies (eg, on Afro American population for the FDA or on Japanese population for the Pharmaceuticals and Medical Devices Agency in Japan). They will not be collected in the countries where this is prohibited by local regulation.

- Participants will be assigned a unique identifier by the Sponsor. Any participant records or datasets that are transferred to the Sponsor or its service providers will be identifiable only by the unique identifier; participant names or any information which would make the participant identifiable will not be transferred to the Sponsor.
- The participant must be informed that his/her personal study-related data will be used by the Sponsor in accordance with local data protection law. The level of disclosure must also be explained to the participant as described in the ICF/assent form.

- The participant must be informed that his/her medical records may be examined by Clinical Quality Assurance auditors or other authorized personnel appointed by the Sponsor, by appropriate IRB/IEC members, and by inspectors from regulatory authorities.
- Participants must be informed that their study-related data will be used for the whole “drug development program”, ie, for this trial as well as for the following steps necessary for the development of the investigational product, including to support negotiations with payers and publication of results.

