1 INTRODUCTION

1.1 STUDY DESIGN

This is a Phase 3, multicenter, 52-week treatment, parallel-group, double-blind, randomized, placebo-controlled study to investigate the efficacy of dupilumab in adults and pediatrics aged 6 years and older with signs and symptoms of AFRS.

After a screening phase of 2 to 4 weeks, approximately 62 participants with AFRS who satisfy the inclusion and exclusion criteria will be centrally randomized (using permuted block randomization schedule) via Interactive Response Technology (IRT) in a 1:1 ratio to receive either dupilumab or matching placebo. Randomization will be stratified first by age (adults versus adolescents/children [≥ 6 years old]). In adults, randomization will be stratified further by time from last surgery (≤ 2 years [including surgery naive participants], > 2 years), disease pattern (unilateral/bilateral in the endoscopy at screening), and country. In adolescents/children, randomization will not be stratified further.

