5.3 APPENDIX 3 DEMOGRAPHICS AND BASELINE CHARACTERISTICS, PRIOR OR CONCOMITANT MEDICATIONS

Demographics, baseline characteristics, medical surgical history

The following demographics and baseline characteristics, medical and surgical history and disease characteristics at baseline will be summarized using descriptive statistics in the randomized population.

Demographic and baseline characteristics

- age in years as quantitative variable and in categories (≥ 6 - <12 , ≥ 12 - <18 , ≥ 18 - <65 , ≥ 65 years)
- gender (Male, Female)
- Race (American Indian or Alaska Native, Asian, Japanese, Black or African American, Native Hawaiian or Other Pacific Islander, White, Not reported, Unknown)
- Ethnicity (Hispanic or Latino, Not Hispanic or Latino, Not reported, Unknown)
- Region (Americas: Argentina, USA, Canada; Asia: China, Japan, India, Turkey, Saudi Arabia)
- Baseline weight (<70 , ≥ 70 - <90 , ≥ 90 kg)
- Baseline BMI (<27 , ≥ 27 kg/m²)

Baseline safety and efficacy parameters (apart from those listed above) will be presented along with the safety and efficacy summaries.

Medical (or surgical) history includes all the relevant medical (or surgical) history during the lifetime of the participant. Medical and surgical history will be coded to a LLT, PT, HLT, HLGT, and associated primary SOC using the MedDRA version currently in effect at Sanofi at the time of database lock. Allergic comorbidities will be summarized separately.

Disease characteristics at baseline

- Nasal polyp score
- Lund-Mackay score
- Nasal symptom diary scores for nasal congestion/obstruction, decreased/loss of sense of smell, rhinorrhea (anterior/posterior nasal discharge) and total symptom score (TSS) respectively
- UPSIT smell test score
- SNOT-22
- Time since first diagnosis of AFRS (years) to be derived as
(Year of randomization – Year of first diagnosis of AFRS) + (month of randomization – month of first diagnosis of AFRS)/12
- Age at onset of AFRS (years)
- Number of prior sino-nasal surgeries (0, 1, 2, ≥ 3)
- Time from last sino-nasal surgery (≤ 2 years [including surgery naive participants], >2 years) to be derived as
(Year of randomization – Year of last sino-nasal surgery) + (month of randomization – month of last sino-nasal surgery)/12
- Disease pattern (unilateral/bilateral in the endoscopy at baseline)
- Asthma comorbidity (Yes, No)

For asthma patients, provide the following:

- Age at onset of asthma (years), identified as investigator reported in the eCRF.

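### The ethnicity subgroup of the primary endpoint places participants of unknown ethnicity with Hispanic or Latino participants and gives Not reported no place, so the ethnicity contrast may be diluted

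*SAP*

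**What the plan says.** SAP 3.7.2 gives the purpose of these analyses: "Subgroup analyses of the primary efficacy endpoint will be performed to assess the homogeneity of the treatment effect across the following subgroups". For ethnicity the levels are "Ethnicity (Hispanic or Latino or unknown, Not Hispanic or Latino". The model is the primary ANCOVA with two additions: "Treatment-by-subgroup interaction term and the subgroup factor term will be added in the primary model". The output is described as follows: "In each subgroup, the treatment effects (dupilumab versus placebo) for the primary endpoint will be provided, as well as the corresponding 95% CI", together with forest plots. The same section has a general provision for sparse levels: "categories with fewer than 5 participants may be combined with other categories".

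The baseline tables in SAP 5.3 (Appendix 3) use four values: "Ethnicity (Hispanic or Latino, Not Hispanic or Latino, Not reported, Unknown".

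Protocol 10.1.4 says of race and ethnicity data: "They will not be collected in the countries where this is prohibited by local regulation".

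Protocol 9.4.2 names age group, gender and region as subgroup factors and leaves any others to the SAP, so the ethnicity levels are defined only in SAP 3.7.2.

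**The concern.** A homogeneity analysis compares the treatment effect between groups whose membership is known. Unknown is not an ethnicity. Assigning it to the Hispanic or Latino level amounts to imputing one fixed value for every participant whose ethnicity is missing, with no argument that this value is the likely one. Any unknown participant who is in truth not Hispanic or Latino is then counted on the wrong side. If such participants respond like the rest of the non-Hispanic group, the two rows of the forest plot are drawn together and the interaction estimate shrinks. The analysis would then lean towards the homogeneity that it is meant to examine.

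The rule is also incomplete. A participant recorded as Not reported fits neither level, so a programmer would have to decide whether to pool or drop that participant.

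At stake is how one row of a supportive forest plot, and the interaction behind it, can be read.

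**Working it through.** **The passages side by side.**

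| Value in SAP 5.3 | Place in the SAP 3.7.2 subgroup |
|---|---|
| Hispanic or Latino | first level |
| Not Hispanic or Latino | second level |
| Unknown | first level, whatever the count |
| Not reported | none stated |

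The baseline table shows that the SAP intends to keep the four values apart. The provision for sparse levels does not explain the pooling: it is optional and depends on counts, whereas the pooling of Unknown is fixed. That provision also does not say which level absorbs a small one.

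**Size of the dilution.** The documents state no figure on this point, so there is nothing to reproduce. They give no ethnicity counts either, so every count below is an assumption. Let

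- n_H = number Hispanic or Latino,
- n_U = number unknown,
- q = share of the unknowns who are in truth not Hispanic or Latino,
- m = q × n_U / (n_H + n_U), the share of the pooled level who are not Hispanic or Latino.

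Assume balanced treatment groups within the level, and that unknowns who are not Hispanic or Latino have the same treatment effect as the known non-Hispanic group. Then

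pooled effect = (1 − m) × effect in Hispanic + m × effect in non-Hispanic.

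Subtracting the non-Hispanic effect gives

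observed contrast = (1 − m) × true contrast.

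For example, with n_H = 5, n_U = 2 and q = 1, m = 2/7 = 0.286 and 71% of the contrast is kept.

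| n_H + n_U | kept if q = 1 | kept if q = 0.5 |
|---|---|---|
| 10 + 1 | 91% | 95% |
| 10 + 5 | 67% | 83% |
| 5 + 2 | 71% | 86% |
| 5 + 5 | 50% | 75% |
| 3 + 5 | 38% | 69% |

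If n_U = 0 or q = 0, then m = 0 and nothing is lost.

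**Precision of the row.** SAP 1.1 plans "approximately 62 participants with AFRS who satisfy the inclusion and exclusion criteria", randomized 1:1. For a subgroup of n split equally between treatments, the approximate 95% CI half-width in SD units is 1.96 × √(4/n). For n = 10 this is 1.96 × 0.632 = 1.24 SD; for n = 20 it is 1.96 × 0.447 = 0.88 SD. The row is imprecise with or without the pooling.

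**The case against.** Five points can be made for the plan.

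- **The label is open.** The level is named as including unknowns. A reader might call the row mislabelled, but the documents do not support that. It would mislead only if the output, or a later reader, dropped the second half of the name. This point stands.
- **The composition will be visible.** The SAP 5.3 table reports the four values separately, so anyone can see how many unknowns there are. This stands too, but it does not let the reader separate the treatment effects.
- **The link to country is not established.** From Protocol 10.1.4 a reader might infer that whole countries would be swept into the Hispanic or Latino row. Neither document names a country where collection is prohibited, or says whether a value not collected is coded Unknown, Not reported or blank. The clause shows only that missing ethnicity is foreseen.
- **Fixing the levels in advance is good practice.** It limits grouping after the data are seen. That is true, but it does not justify the particular grouping chosen, and a cleaner one can be fixed in advance equally well.
- **Nothing decisive depends on it.** Ethnicity is not a term in the primary model (SAP 3.2.2), it does not appear in the hierarchy of SAP 3.5, and the trial is judged positive on the primary endpoint alone. No separate claim for Hispanic participants is planned. This stands and sets the weight of the point.

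**Conclusion.** The point holds as a minor one. SAP 3.7.2 puts a missing-data state into one of the two groups being compared, gives no reason, and leaves Not reported without a place. If there are unknowns and some are not Hispanic or Latino, the effect for that level is a mixture and the ethnicity contrast is diluted. In the illustrative cases above, between 38% and 95% of the contrast is kept. The loss is nil if there are no unknowns.

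The direction, towards homogeneity, rests on the assumption that the misplaced unknowns respond like the known non-Hispanic group. The size rests on counts that the documents do not give. A reader might want the shift expressed in LMK points, but the documents give neither the counts nor any difference in effect by ethnicity, so no such figure can be supported.

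The primary estimate, its p-value, the overall alpha and the testing hierarchy are unaffected. The gain is a cleaner supportive analysis, not a different trial conclusion.

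**What to change.** In SAP 3.7.2:

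1. Define the comparison as Hispanic or Latino versus Not Hispanic or Latino.
2. Leave participants recorded as Unknown or Not reported out of the ethnicity interaction model and display their count beside the forest plot. Alternatively, show them together as a separate row.
3. State that the fewer-than-5 provision does not allow Unknown or Not reported to be merged into a known ethnicity. Without this, a small separate row could be folded back into Hispanic or Latino and the problem would return.

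The cost is one SAP line. No new data are needed, and the imputed datasets are those already saved from the primary analysis. If unknowns are left out, this one supportive subgroup analysis has slightly fewer participants; the ITT primary analysis keeps everyone.
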